## 1 Protocol version control

Version number	Version Date	Protocol approvals and dates (e.g. REC etc)	Supersedes approved version number/date
DRAFT	02.11.19	For ethical approval	Not applicable

### **3** Abbreviations

- ACR American college of rheumatology
- BSG Behavioural Sciences Group
- COREQ Consolidated criteria for reporting qualitative research
- HCP Health Care Professional
- MCTD Mixed connective tissue disease
- PPI Patient and Public Involvement
- RA Rheumatoid arthritis
- SLE Systemic Lupus Erythematosus
- SLICC Systemic Lupus International Collaborating Clinics
- UCTD Undifferentiated connective tissue disease

## 4 Study Synopsis

Study title	The LISTEN study
	Listening: Involving SLE patients To Empower and Negotiate recognition
Short title	The LISTEN study
Chief Investigator	[name]
Chief Investigator's employing Institution	University of Cambridge
Funder	LUPUS UK
Study Duration	Phase 1 – small support email groups – duration 4 months, followed by questionnaire at 12 months after randomisation
	Phase 2A – Updated questionnaires to physicians, all LUPUS UK members, healthy control group and available online to RA and fibromyalgia patients. Response collection and analysis – 6 months
	Phase 2B – Interviews with physicians and patients – 6 months
	Total study duration (phases will overlap) – approx. 16 months
Participants	Phase 1 - Patients with SLE, UCTD, discoid/cutaneous lupus, Sjögren's syndrome or MCTD/Overlap disease responding to an invitation to complete online questionnaire introduced by online forums and support groups moderators.
	Phase 2A – All LUPUS UK members. RA questionnaire – ppts with self- verified RA. Fibromyalgia – ppts with self-verified fibromyalgia (available online on HealthUnlocked) Healthy friends – nominated friends of LUPUS UK members. Randomly selected physicians to receive physician questionnaire.
	Phase 2B – Purposively selected physicians and patients for interviews
Sample size	Phase 1 – Email support groups (180)
	60 in each of three groups
	Phase 2A – Questionnaire to all LUPUS UK members (5500), made available online on RA and fibromyalgia forums (expected 200 responses per disease category), link given by lupus forum members to healthy friends (expected 300 responses). Physician questionnaires (260)
	Phase 2B – Interviews until theoretical saturation reached. Estimated 15-25.
Objectives	1. To explore the acceptability and feasibility of peer support by small group email.
	2. To measure the impact of peer support and research involvement on the mental health, wellbeing, self-esteem and disease acceptance of patients with systemic autoimmune rheumatic diseases
	3. To empower patients and improve research quality and relevance by actively involving them in research into their own disease; generating

	research questions and research materials that are relevant to their priorities, needs and experiences.							
	4. To investigate key factors in effects of the disease and patient-physician interactions pre and post diagnosis on patient behaviour, mental health/ wellbeing and disease acceptance							
	5. To compare lupus and related disease patients' wellbeing, mental health and perception of medical care with patients with RA, fibromyalgia and healthy friend controls							
Eligibility criteria	Participants aged 18 years or over							
	UK residents							
	• Participants with self- verified SLE, UCTD, discoid/cutaneous lupus, Sjögren's syndrome or MCTD/ Overlap disease.							
	• Phase 2 – Also includes Ppts with RA, fibromyalgia and healthy controls ('healthy controls' excluded if any significant chronic or acute severe illness)							
	• Physician questionnaires and interviews eligibility: A consultant or GP currently practising in the UK							
Description of intervention	
 
Phase 1 questionnaire will be made available through the online platform Qualtrics on LUPUS UK forum, lupus UK sufferers Facebook page and other online health forums if recruitment insufficient. This questionnaire contains questions on the impact of the disease and support on their wellbeing and mental health.
 
							
	2. Questionnaire respondents will be randomly allocated into one of 3 groups: Gps A and B will be divided into email support groups of 5-6 Ppts with the aim to provide peer support. In addition, Gp A will be given research tasks to discuss, including the pilot questionnaire to redesign in order to distribute to all LUPUS UK members. Gp C will be the control group.							
	3. The email support groups will communicate for 4 months, a which time all 3 Gps will receive another questionnaire to ascer any changes to their mental health, wellbeing, support perception and acceptance. They will also be asked to evaluate the posi and negative aspects of the group support. Another questionnaire will be sent 12 months after baseline questionnaire							
	4. The patient-adapted questionnaire will be made available online and by post to LUPUS UK members and online groups, including the RA and fibromyalgia forums and an adapted questionnaire link given to healthy friends by forum members. The physician questionnaire will be sent to a random sample of consultants and GPs. These questionnaires will contain questions on perceptions of support, wellbeing, mental health, medical relationships and patient behaviour.							
	
 
In-depth interviews will be carried out with purposively selected participants from questionnaire responses.
 
							
Analysis	Qualitative - Thematic analysis including using Nvivo software							

Quantitative - Descriptive s	statistics, ANOVA and	d correlations/ regressions.

### 5 Study background and rationale

#### **Background**

Previous studies and our current work with SLE and related autoimmune diseases patients have identified a clear and urgent need for patient-focused research further exploring the psychological impact and changes in patient behaviour from the often lengthy diagnostic delays, misdiagnoses and perceptions of level of support. The exploratory phase involved an online pilot questionnaire, in-depth interviews with purposively selected patients and an analysis of the forum. This found a majority of participants reporting significant – and often ongoing- psychological distress from their medical encounters, predominately during the diagnostic journey but also post diagnosis. The widespread loss of trust in the medical profession from the diagnostic journey has serious implications as trust is widely reported to be associated with adherence to treatment, improved quality of life, satisfaction with care and better health outcomes.

A US study of over 3000 SLE patients found that over 50% were initially told there was nothing wrong or symptoms were psychological.  70% of participants in our phase 1 survey stated that a psychological misdiagnosis felt worse than being misdiagnosed with another disease with 84% reporting it reduced their trust in doctors in the future and 87% reporting it changed their behaviour in seeking medical help in the future. An earlier (2014) survey of over 2500 Lupus UK members found the mean time to diagnosis from initial symptoms was 6.4 years with approximately half reporting they were initially misdiagnosed. This study and our pilot study highlights the urgent necessity of an agenda for patient focused research. These studies will assist with highlighting to HCPs (Health care professionals) the often extremely damaging impact of the diagnostic uncertainly period and the influence physician behaviour has on patient mental health and behaviour pre and post diagnosis. More support prior to diagnosis is essential to improve the current situation for all undiagnosed rare disease patients on their often long and complicated medical journeys

Delays in SLE diagnosis and therefore treatment are associated with a worse physical prognosis as morbidity and mortality are improved by early use of hydroxychloroquine and an immunosuppressive regime. The perception of poor care on the diagnostic journey, especially for the many who report feeling their symptoms were disbelieved, can have a continued influence on a patient's mental health and behaviour, thus also potentially damaging their physical health, long after the correct diagnosis. Insecurity, fear of rejection and physician's disbelief were widely reported by these patients in phase 1 to be always present even in subsequent positive medical relationships. This was also found in a study of parents of children with autoinflammatory disease where they reported becoming increasingly fearful, confused, lost self-confidence and began doubting their own judgement in the face of medical establishment even after diagnosis. Studies of other diseases with lengthy diagnostic journeys have demonstrated the perceptions of stress, isolation and exclusion that worsens with the chaotic journey through numerous referrals, investigations and disease evolutions.

With no definitive test for SLE and related systemic autoimmune rheumatic diseases, a diversity of manifestations and often non-specific presenting symptoms, patients are reliant on expert opinion in diagnosing the disease. Studies report that teaching in medical schools is inadequate, medical students lack confidence in diagnosing musculoskeletal disorders, there is a lack of rheumatological experience in GP training and teaching does not reflect the impact of rheumatological conditions. Other studies have also highlighted the need for increased emphasis on musculoskeletal disorders in medical teaching to increase accurate rheumatology referrals and more awareness of SLE amongst all HCPs to aid faster diagnosis. Analysing and publishing the patient perspectives is key to improving understanding and educating both clinicians and patients.

SLE and related autoimmune diseases are often reputed to be an 'invisible' disease with both social and medical diagnoses seemingly reliant upon the ability to see illness, with an often prolonged period of time before symptoms are validated by a diagnosis. Validation is a key theme identified in both the existing literature and our recent research. Santiago et al found that invalidation occurred in all

rheumatic diseases with psychological factors, loneliness and pain intensity associated with invalidation and deserving of dedicated intervention. Our initial research is in agreement with previous research that the reliance amongst many HCPs on often inconclusive test results rather than considering subjective symptoms can leave many patients feeling disbelieved and dismissed. Price and Walker found that for some the SLE diagnostic journey often has no satisfying conclusion and can be an iatrogenic experience with the journey to diagnosis mirroring the disease in terms of ambiguity and chaos. The ambiguous complexity of SLE and other related autoimmune diseases causes difficulty with the desire for clarity and certainty  with insecurity and uncertainty identified in both physicians and patients.

Without a mutually trusting relationship, patients are more likely to not adhere to medication regimes and not inform their physician of changes to medication and symptoms. Only 53% of those who stopped/altered their medication in the phase 1 survey reported that they always informed their rheumatologist. Previous studies show non-adherence for reasons including lack of understanding, fear of adverse effects and perception that the medications are not effective, sometimes leading to discontinuation without physician advice or approval. Our questionnaire results also demonstrate that the cognitive impairment common in SLE patients leads to frequent non-intentional non -adherence as a significant proportion of patients reported memory difficulties and forgetting medications at times. Poor adherence is difficult to evaluate with reported rates in SLE varying from 3%-85% between studies  so quantifying non-adherence in this large study and exploring this from the perspective of both the patients and clinicians will provide valuable insight into methods of improving adherence, such as good communication, patient involvement in medication decisions memory aids and trust in the medical profession.

Under-reporting has also been frequently raised in phase I in terms of general SLE symptoms, seemingly related to patients' frequently expressed fear of being viewed as a '*hypochondriac*' due partly to the diversity, changeability and quantity of symptoms but predominantly due to previous non-organic or psychosomatic misdiagnoses. This avoidance of reporting symptoms has been discussed by patients as particularly likely for any mental health issues arising amongst those whose SLE was originally misdiagnosed as mental health problems, such as depression or anxiety and requires further investigation. Approximately 1/5 to 1/2 of rheumatological patients have psychosocial problems due to their disease and these are frequently not reported or detected by their physician. In the 2011 (US) National burden of lupus survey, 52% of lupus patients reported they minimise symptoms when reporting to physicians yet 72% of physicians were unaware of this tendency to underreport. Quantifying this under-reporting from the large-scale questionnaire proposed for phase 2, comparing with the proposed physician's questionnaire and correlating with variables such as length of diagnostic journey and reported level of trust in physicians will allow a much deeper understanding to help design targeted interventions for the most vulnerable.

Relationships between HCPs and patients have altered in recent years with decreasing automatic trust among patients in the advice of doctors. Patients value communication, information and use of evidence to support decisions with encouragement of questioning and obtaining information about their condition. Empathetic listening and belief in the patient's subjective reporting of symptoms was highlighted as the top patient priority – yet often felt to be unsatisfactory - in this phase 1 study and other studies of rheumatic diseases. Patients in phase 1 have reported that there is often a disparity in priorities between wanting to discuss with physicians their quality of life (with the most frequent and debilitating concerns being fatigue, cognitive difficulties and pain) whilst some physicians are reported to be more focused on check lists of symptoms and discussing medications. Gordon et al found a substantial burden of disease in SLE patients, with most (82.5%) reporting fatigue, which was associated with a significantly reduced quality of life. This study highlighted that further work is needed to educate HCPs on the consequences of reduced quality of life.

Lazare et al highlight the three inter-linked functions of medical encounters: to gather information, develop and maintain a therapeutic relationship and communicate information. The quality of the relationship is the major influence on patient and physician satisfaction. It also largely determines the quality and quantity of information elicited and comprehended as a patient who is anxious from previous poor interactions may not comprehend information clearly and a patient who feels distrust or dislike for the physician/ physicians may not disclose information or comply with recommendations. Patients in phase 1 regularly report both high anxiety during medical encounters and reduced trust in physicians.

As rheumatic diseases are chronic, patient- physician relationships need to be established and maintained for the patient's lifetime with the phase 1 study reporting increased trust from continuity of care and often great attachment to the physician who diagnosed and first '*believed*' them. Those with long standing chronic rheumatological diseases desire to work with physicians from a position of mutual respect and trust with a qualitative study of rheumatoid arthritis patients finding that they felt it was important in building a trusting relationship that the physicians acknowledged the patient's expert knowledge and admitted openly to areas where they themselves lacked knowledge.  This has also been highlighted as a key point from the phase 1 forum analysis, questionnaires and interviews where participants regularly identified the difficulties of negotiating the doctor-patient relationship where they have significant knowledge of their own disease. This research will allow a deeper understanding of patient and physician views of methods of developing positive medical relationship where the patient can feel trust and security leading to improved physician and self-management with associated improved outcomes in physical and mental health. '*Insecurity*' was the key over-riding theme found in all methodology from our preliminary studies, both in terms of uncertainty of the disease course and in medical relationships.

Despite the WHO action plan for chronic disease management encouraging governments to provide education, incentives and tools for self-management and care, many patients with lupus report there is limited assistance with self-management education from medical sources, thus often relying on peers in online forums and Facebook groups for knowledge transfer and emotional support. Peer support from those who experience the same challenges of living with the same chronic health condition is increasingly being researched in terms of measuring health outcomes, improved adherence to treatment, empowerment, psychological outcomes and improved quality of life.

Studies have shown varied success from peer support initiatives across multiple disease types with a recent systematic review finding 4 out of 6 RCTs reporting no statistically significant differences in measured outcomes in heart disease patients comparing usual care with peer support. Another study found no significant difference in wellbeing scores in diabetes patients provided with peer support in addition to usual care. However, improvements have been reported from other studies including improved adherence from peer support interventions in HIV patients. Studies have also demonstrated that peer education can be as effective as professional training in diabetes patients.

The WHO is also increasingly recognising the importance of mental wellbeing as an important component of health. This study will measure the impact of small group peer support on mental wellbeing and the large-scale questionnaire will determine the current state of mental wellbeing and perceptions of support, in a significant proportion of patients with systemic autoimmune rheumatic diseases in the UK.

### 6. The 'LISTEN' study

#### 6.1 Study objectives

The main aims of the study are:

1. To explore the acceptability and feasibility of peer support by small group email.

2. To measure the impact of peer support and research involvement on the mental health, wellbeing, self-esteem and disease acceptance of patients with systemic autoimmune rheumatic diseases.

3. To empower patients and improve research quality and relevance by actively involving them in research into their own disease; generating research questions and research materials that are relevant to their priorities, needs and experiences.

4. To investigate key factors in effects of the disease and patient-physician interactions pre and post diagnosis on patient behaviour, mental health/ wellbeing and disease acceptance.

5. To compare lupus and related disease patients' wellbeing, mental health and perception of medical care with patients with RA, fibromyalgia and healthy controls.

#### 6.2 Inclusion Criteria

Patients can be included in the study if they meet all of the inclusion criteria below:

- Participants with a self-verified diagnosis of SLE, UCTD, Sjögren's syndrome, discoid/cutaneous lupus or MCTD/overlap disease.
- Resident in the UK.
- Participants aged 18 or over.
- Additional Ppts for phase 2 includes those with self-verified RA or fibromyalgia, resident in UK and aged 18 or over. Healthy controls must be resident in UK, aged 18 or over and have no significant chronic or acute illness.
- Physician participants must be Consultants or General Practitioners currently practising in the UK.

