#### 6.3 Participant recruitment

Following ethical approval, patients will be approached by joint message on the LUPUS UK HealthUnlocked forum by LUPUS UK and research staff, with the study information detailed and the participant information sheet attached. A minimum of 24 hours will be left before the consent form and questionnaire are made available on the site. Consent will be returned with the questionnaire. We require 180 participants. If recruitment numbers are not satisfactory, prospective ppts will be approached through lupus UK support groups, other health forums and LUPUS UK Facebook page.

Phase 2 questionnaires and/or the online link will be sent to all LUPUS UK members by email and/or post with information sheets and made available online. The adapted versions for RA and fibromyalgia Ppts will be made available on the RA and fibromyalgia HealthUnlocked forum with an information sheet. Healthy friend controls will be recruited by Ppts with lupus/ related disease giving a friend the online link to their information sheet and questionnaire.

Physicians will be randomly selected, stratified by UK location. They will be approached by email, with contact details of the study team, a participant information sheet and online link to a questionnaire.

Purposive sampling will be used to select participants for interview from those who have given consent for this on their questionnaire response.

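### RA and fibromyalgia comparators may also have lupus-related disease, and no rule classifies people with both diagnoses, so the Objective 5 contrasts can be distorted in either direction

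*Protocol*

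**What the plan says.** Objective 5 (section 6.1) is a between-group comparison: "To compare lupus and related disease patients' wellbeing, mental health and perception of medical care with patients with RA, fibromyalgia and healthy controls".

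Section 6.2 defines the groups.

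- Lupus-related group: "Participants with a self-verified diagnosis of SLE, UCTD, Sjögren's syndrome, discoid/cutaneous lupus or MCTD/overlap disease". Freedom from RA or fibromyalgia is not required.
- Disease comparators: "Additional Ppts for phase 2 includes those with self-verified RA or fibromyalgia, resident in UK and aged 18 or over". Freedom from lupus-related disease is not required.
- Healthy controls: "Healthy controls must be resident in UK, aged 18 or over and have no significant chronic or acute illness". This is the only health-status exclusion.

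The eligibility row of the Synopsis (section 4) follows the same pattern: "Also includes Ppts with RA, fibromyalgia and healthy controls ('healthy controls' excluded if any significant chronic or acute severe illness".

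Section 6.3 describes separate routes. The lupus group is reached directly and also over the internet: "Phase 2 questionnaires and/or the online link will be sent to all LUPUS UK members by email and/or post with information sheets and made available". For the comparators, "The adapted versions for RA and fibromyalgia Ppts will be made available on the RA and fibromyalgia HealthUnlocked forum with an information sheet". The LUPUS UK forum, used for Phase 1 recruitment, is also on HealthUnlocked.

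The Synopsis expects 200 responses in each of RA and fibromyalgia and plans to send the lupus questionnaire to 5500 members. Section 7.3 gives each participant a study code but describes no check for the same person under two versions.

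**The concern.** A comparison between diseases needs a rule for people who have more than one of them. The authors saw this for healthy controls and wrote an exclusion. For RA and fibromyalgia there is neither an exclusion nor a classification rule, although all diagnoses are self-verified and the index group itself includes overlap disease.

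A person with both diagnoses can be counted as lupus, as comparator, or twice. The lupus-RA and lupus-fibromyalgia differences then depend partly on how such people happened to be sorted, and a reader cannot tell how much of any difference, or lack of one, comes from that. If the questionnaires do not record all the relevant diagnoses, this cannot be undone once collection closes.

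**Working it through.** **Eligibility check.** Take a UK resident aged 18 or over with self-verified Sjögren's syndrome and self-verified fibromyalgia, and apply section 6.2. The lupus-related criterion is met. The fibromyalgia criterion is met. The healthy-control exclusion does not apply. The Synopsis gives the same result. Sections 6.3, 6.6, 6.7 and 7.3 contain no priority between diagnoses, no dual-diagnosis category and no one-response rule.

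**Inputs.** The protocol states no effect size, SD, power or dual-diagnosis rate for the Phase 2 contrasts, so there is no stated figure to reproduce. From the Synopsis: 200 expected per comparator and 5500 lupus questionnaires sent (response rate not stated). Assumed for illustration: q of 5% to 30%, SD of 1, two-sided 5% level.

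**Size and direction.** Set the lupus-group mean at 0. Let Δ be the mean of comparators without lupus-related disease, and m the mean of dual-diagnosis respondents who sit in the comparator group. Then

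observed difference = (1 − q)Δ + q·m.

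*Case 1, dual-diagnosis respondents score like the lupus group (m = 0), Δ = 0.30 SD:*

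- q = 0.10: 0.90 × 0.30 = 0.27
- q = 0.20: 0.80 × 0.30 = 0.24
- q = 0.30: 0.70 × 0.30 = 0.21

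*Case 2, they do not, Δ = 0.25 SD and q = 0.20:*

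- m = −0.5: 0.20 − 0.10 = 0.10
- m = 0: 0.20
- m = +0.5: 0.20 + 0.10 = 0.30, larger than the true 0.25

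The overlap also runs the other way. Now put the lupus-only mean at 0 and measure Δ and m from it. If a share r of the lupus group has both diagnoses, the observed difference is (1 − q)Δ + (q − r)m. The sign of the second term depends on q, r and m, none of which the protocol gives.

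**Precision under case 1.** With 200 per group, the difference detectable with 80% power is (1.960 + 0.842) × √(1/200 + 1/200) = 0.28 SD; with 5500 lupus respondents it is 0.20 SD. Diluting that difference by (1 − q) gives power Φ(2.802(1 − q) − 1.960), whatever the lupus number. Regaining 80% at the same group ratio needs 200/(1 − q)² comparators.

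| q | Power | Comparators for 80% |
|---|---|---|
| 0 | 80% | 200 |
| 5% | 75.9% | 222 |
| 10% | 71.3% | 247 |
| 20% | 61.1% | 313 |
| 30% | 50.0% | 409 |

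**What separating them costs.** Suppose q = 20% and both groups of 200 lose 20%, leaving 160 each. The undiluted 0.28 SD then has power Φ(0.280/√(2/160) − 1.960) = Φ(0.546) = 71%, against 61% when dual-diagnosis respondents are left among the comparators.

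**The case against.** Much can be said on the other side, and part of it stands.

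- **Group by link.** A reader might infer that group is fixed by whichever link was opened. Section 6.3 says only where each version is posted. No other assignment rule is given, but this one is not stated either.
- **Independence.** A reader might infer that the analysis assumes distinct, independent groups. The Synopsis names ANOVA, and section 6.7 names multiple regression and summaries stratified by characteristics and group. Regression could carry a co-diagnosis term. If one person's two answers correlate positively, the variance of the difference falls, so an ordinary two-sample test would tend to be conservative.
- **Always toward zero.** Dilution is certain only if dual-diagnosis respondents score like the lupus group. Case 2 above shows inflation when they do not.
- **A null result could not be interpreted.** This does not follow. At q of 10% to 30% under case 1, 70% to 90% of the difference survives, and the true q could be small.
- **Choice of estimand.** A person with RA and Sjögren's syndrome does have RA, and comparing patient populations as they present is a legitimate descriptive aim. That stands, but the protocol should then say so.
- **Other documents.** The Phase 2 questionnaire was still to be redesigned and may ask about other diagnoses. A statistical analysis plan could handle duplicates, and the record linking codes to contact details offers a means. Group definition, however, belongs to eligibility, which section 6.2 sets, and no later plan can separate people whose diagnoses were not recorded.

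**Conclusion.** The point holds in this form: as written, the criteria let the comparator and lupus-related groups overlap, and nothing in the protocol classifies people in the overlap or limits them to one response. The lupus-RA and lupus-fibromyalgia contrasts can be distorted. Under the assumption that dual-diagnosis respondents score like the lupus group, the loss is the factor (1 − q): 0.30 SD becomes 0.27 to 0.21 SD at an assumed q of 10% to 30%. Without that assumption the direction is open. The true size is unknown because the protocol gives no q.

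The documents do not support saying that the bias must be toward zero, that the analysis necessarily treats the groups as independent, or that a finding of no difference would be worthless. The consequence is confined to the RA and fibromyalgia contrasts in Objective 5, one of five aims. The Phase 1 randomised comparison and its primary outcome are untouched. It should be corrected before the Phase 2 questionnaires go out, because the information cannot easily be recovered afterwards.

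**What to change.** 1. Put the same checklist of all relevant diagnoses in every Phase 2 patient questionnaire: SLE, UCTD, discoid/cutaneous lupus, Sjögren's syndrome, MCTD/overlap, RA and fibromyalgia.
2. Ask in each version whether the respondent has already completed another one, and keep one record per person.
3. State in section 6.2 that group is assigned by reported diagnosis, with dual-diagnosis respondents in a separate, pre-specified category.
4. Make the main Objective 5 contrasts lupus-related disease without RA or fibromyalgia against RA or fibromyalgia without lupus-related disease. Add a sensitivity analysis that includes the dual-diagnosis respondents.

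The separate category is preferable to removing dual-diagnosis people from the comparators alone. That would keep them in the lupus group, treat the two sides differently, and could itself create or enlarge a difference.

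The cost is one or two added questions, a short addition to section 6.2, and a modest loss of responses from the main contrasts.
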